6.3.2 Blood samples

During the entire trial, a volume of approximately 40ml blood will be sampled from each participant for research purposes, in addition to standard of care blood samples: ~10ml of blood (2 x5 ml tubes) will be obtained for research purposes at Day 1, Day 7, and Day 90 for evaluation of platelet activation (including D-dimers), coagulation markers, smooth muscle activation markers (soluble CD40/44 ligands, and ERK ½) and inflammation markers.

All research blood samples will be processed and stored in a freezer at the Thrombosis Group Research Laboratory and analyzed at the conclusion of the study after enrollment has been completed.

6.3.3 Duplex ultrasound arterial examination

Duplex ultrasound arterial examination will be performed at the Ottawa Civic Hospital (Diagnostic Imaging) at 30 days, 6 and 12 months as part of the routine care. The following will be recorded in the CRF : re-stenosis as defined by peak velocity flow, and the Ankle Brachial Index (ABI).

The Ankle Brachial Index(ABI) is the ratio of the blood pressure in the lower legs to the blood pressure in the arms. The ABI is calculated by dividing the systolic blood pressure at the ankle by the systolic blood pressures in the arm.

6.4 WITHDRAWAL / DISCONTINUATION CRITERIA

Participants have the right to withdraw from the study treatment at any time for any reason. The Investigator has the right and obligation to withdraw participants from the study treatment in the event of:

1. Adverse event(s) which would, in the judgment of the investigator, require discontinuation of study product(s)
2. Request by the participant or their legally authorized representative (consent withdrawal)
3. Non compliance to the study protocol
4. Participants needs additional medication that would interfere with the study
5. Participant is lost to follow-up

6. The sponsor, or the principal investigator or the Data and Safety Monitoring Board or a government agency such as Health Canada cancels the study.

When a participant withdraws consent after starting the protocol treatment the investigator or delegate should make every effort to contact the participant to determine, as completely as possible, the reason for the withdrawal and to schedule an end-of-study visit for assessing potential adverse events. The participant will be asked to return unused study products and will be switched to standard of care, as per their own treating physician.

6.5 MANAGEMENT OF MAJOR BLEEDING

All participants with major bleeding will have study drug held until judged safe to resume by the investigator.

6.5.1 Treatment arm 1

In the event of hemorrhagic complications in a participant receiving Rivaroxaban, treatment should be temporarily discontinued, and the source of bleeding investigated. Rivaroxaban has a half-life of approximately 5 to 13 hours. Consideration should be given to the resumption of antithrombotic therapy at the discretion of the treating physicians, when clinically appropriate to adequately control risk of underlying thrombosis.

Management of bleeding should be individualized according to the severity and location of the bleeding. Appropriate symptomatic treatment should be used as needed, such as mechanical compression (eg, for severe epistaxis), surgical hemostasis with bleeding control procedures, fluid replacement and hemodynamic support, blood products (packed red cells or fresh frozen plasma, depending on associated anemia or coagulopathy) or platelets.

If bleeding cannot be controlled by the above measures, consider administration of one of the following pro-coagulants:

- activated prothrombin complex concentrate (APCC), eg., FEIBA
- prothrombin complex concentrate (PCC)
- recombinant Factor-VIIa (rFVIIa)

However, there is currently only very limited experience with the use of these products in individuals receiving Rivaroxaban. A specific antidote for Rivaroxaban is not available.

6.5.2 Treatment arm 2

In the event of hemorrhagic complications in a participant receiving Clopidogrel, treatment should be temporarily discontinued, and the source of bleeding investigated. A specific antidote for Clopidogrel is not available.

Management of bleeding should be individualized according to the severity and location of the hemorrhage. Appropriate symptomatic treatment should be used as needed, such as mechanical compression (eg, for severe epistaxis), surgical hemostasis with bleeding control procedures, fluid replacement and hemodynamic support, blood products (packed red cells or fresh frozen plasma, depending on associated anemia or coagulopathy).

Platelet transfusion may be used to reverse the pharmacological effects of clopidogrel and aspirin when quick reversal is required.

7 SAFETY

The adverse event reporting period will begin with the first dose of study medication and end on day 90 (at least 48 hours after last dose of study medication). Adverse events may be collected from participant report or by review of the clinical chart. Adverse events will be documented in the CRF.

Clinical investigators and ultimately the Qualified Investigator (QI) have the primary responsibility for adverse event identification, documentation, grading, assignment of attribution and reporting.

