Design:	This is a pilot study conducted at one center, The Ottawa Hospital. It is a Phase 2 open label randomized controlled trial. Consenting participants, meeting all eligibility criteria will be randomized, post PTA procedure, to one of two groups: Rivaroxaban 2.5 mg BID X 90 days plus ASA 81 mg daily OR Clopidogrel 75 mg daily X 90 days plus ASA 81 mg daily Participants will have study drug dispensed at Day 1 and take medication for 90 days. ASA may be continued after the study, for both groups, as per the standard of care. Visits will occur at 7 days, 30 days, 90 days, 6 months and 12 months. Participants will be followed for 12 months (\pm 14 days) in total. Adverse events will be collected for the first 90 days .
Intervention Description:	Treatment Arm 1 Rivaroxaban 2.5 mg twice daily for 90 days (rivaroxaban will be started 6 to 8 hours after the finalization of the procedure) and 325mg of ASA on day 1 then 81 mg of ASA daily for 89 days Treatment Arm 2 Clopidogrel 300mg on Day 1 (loading dose) then 75 mg daily for 89 days and 325mg of ASA on Day 1, then 81 mg of ASA daily for 89 days
Number of participants:	40

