5.3 TREATMENT ARMS

5.3.1 Treatment Arm 1: Experimental

Rivaroxaban 2.5 mg twice daily for 90 days (rivaroxaban will be started 6 to 8 hours after the finalization of the procedure³⁷) and 325mg of ASA on Day 1, plus 81 mg of ASA daily for 89 days. After 90 days, the study treatment will be discontinued and subsequent treatment will be at the discretion of the attending physician.

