5.3.2 Treatment Arm 2: Standard of care

Clopidogrel 300mg on Day 1 (loading dose), then 75 mg daily for 89 days and 325mg of ASA on Day 1 then 81 mg of ASA daily for 89 days. After 90 days, the study treatment will be discontinued and subsequent treatment will be at the discretion of the attending physician

5.4 PROHIBITED MEDICATIONS DURING THE STUDY:

Systemic treatment with strong CYP 3A4 and P-glycoprotein inhibitors (such as ketoconazole, itraconazole, posaconazole, or ritonavir) is a contra-indication to treatment with Rivaroxaban and is therefore an exclusion criteria for study entry.

If a participant in the rivaroxaban arm requires initiation of treatment with strong CYP 3A4 and P-glycoprotein inhibitor while on study treatment the participant will be withdrawn from study treatment. The participant may then be switched to an alternative anticoagulant treatment at the discretion of the attending physician. See appendix 3 for a list of CYP 3A4 and P glycoprotein inhibitors.

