6.2.4 Study Day 90 (- 14 days)

Data collected :

- Major Cardiac events
- TVR
- TLR
- Amputation
- Bleeding
- AEs
- Compliance
- Concomitant medications
- Blood collection (stored for future evaluation of platelet activation , coagulation markers. smooth muscle activation markers and inflammation markers)

Study treatment will be discontinued and subsequent treatment will be at the discretion of the attending physician (long term use of ASA, as an example).

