APPENDIX 1: SCHEDULE OF EVENTS

	Screening Visit -30 days to -1 day	PTA Baseline Day 1	Visit Day 7 (+/- 3 days)	Visit Day 30 * (+/- 14 days)	Visit Day 90 (- 14 days)	Visit 6 months* (+/-30 days)	Final Visit 12 months* (+/-30 days)
Informed Consent	X						
Inclusion & Exclusion Criteria	X						
Physical Exam ¹	X						
Medical History	X						
Randomization		X					
Dispense study medication		X					
Study medication compliance review			X	X	X		
Rutherford Score	X	X		X		X	X
Review of bleeding events	X	X		X	X	X	X
Review of major cardiac events		X		X	X	X	X
Review of Re-interventions				X	X	X	X
Review of Adverse Events		X	X	X	X	X	X
Clinical Laboratory Tests Results ²	X						
Review of Concomitant Medications	X	X		X	X	X	X
Collect Imaging Outcomes				X		X	X
Blood Work, research samples ³		X	X		X		

¹ Height and weight

² CBC, coagulation tests, and serum creatinine

³ Includes: Platelet activation, coagulation markers, smooth muscle activation, inflammation markers

*Visit may be completed in person or via telephone follow-up

6. SAE status/clinical outcome

- Recovered/Resolved
- Not yet recovered
- Recovered with sequelae
- Fatal/Death
- Unknown

Date & Time:

Date (dd/mmm/yyyy): / /

Time: : (24 hour clock)

7. Event Description

Include a history of the event chronologically including signs and characteristics, severity, dates and outcomes of hospitalization and any other relevant information not captured elsewhere on the form. Include relevant tests/data, treatment/procedures, medical history, treatment history.

8. Relevant tests/data source documents have been attached?

No

Yes

9. Relevant treatment/procedures source documents have been attached?

No

Yes

10. Relevant medical history source documents have been attached?

No

Yes

11. Relevant previous treatment history (including operations or medical procedures) source documents have been attached?

Yes No

12. Study Medication # 1

Study Medication Name: Aspirin

Dose: 81 mg Frequency: once daily

Route: oral

Lot number:

Expiry date (dd/mmm/yyyy): / /

Indication for use: anti-platelet

Date of first dose: (dd/mmm/yyyy): / /

Time of first dose: : (24 hour clock)

Date of last dose prior to SAE: (dd/mmm/yyyy): / /

Time of last dose prior to SAE: : (24 hour clock)

13. Action taken with study drug #1 (Aspirin)

- Temporarily discontinued
- Permanently discontinued
- Nil
- Other:

14. Is there a reasonable possibility that the SAE is related to study drug #1?

- Yes No Not assessable

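### AE reporting cannot both end on day 90 and reach 48 hours after the last dose when dosing runs through day 90, and no AE contact is fixed at or just after the 48-hour point

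*Combined protocol and SAP*

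**What the plan says.** All references are to the combined protocol and SAP.

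- **AE period.** Section 7 has reporting "end on day 90 (at least 48 hours after last dose of study medication". The synopsis gives only the calendar limit: "Adverse events will be collected for the first 90 days".
- **Dosing.** Section 5.3.1 gives "Rivaroxaban 2.5 mg twice daily for 90 days", started 6 to 8 hours after the procedure, with "325mg of ASA on Day 1, plus 81 mg of ASA daily for 89 days". Section 5.3.2 gives "Clopidogrel 300mg on Day 1 (loading dose), then 75 mg daily for 89 days".
- **Closing visit.** Section 6.2.4 is headed "Study Day 90 (- 14 days", and Appendix 1 shows the same window. There is no plus side. Under that visit stands the sentence "Study treatment will be discontinued and subsequent treatment will be at the discretion of the attending physician (long term use of ASA". Section 5.6 places drug return on Day 90.
- **Later contacts.** Sections 6.2.5 and 6.2.6 (months 6 and 12) list bleeding but not AEs. In Appendix 1 the row "Review of Adverse Events" is marked at both months, as is the bleeding row. Section 7.5.1 has participants asked about AEs at every visit.
- **Bleeding endpoints.** Section 8.1.2, items 8 and 9, counts major and minor bleeding from day 1 to day 90.

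**The concern.** The 48-hour clause shows that the protocol means to cover a short tail after the drug is stopped. The calendar clause closes the period before that tail begins if dosing runs its full length. Site staff then have two incompatible rules for whether a day-91 event belongs in the case report form.

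The early-only visit window adds to this. The last AE question that sections 6.2.1 to 6.2.6 schedule inside the AE period can come two weeks before day 90. Whether the participant still has drug to take at that time depends on how section 6.2.4 is read.

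At stake are which bleeds are counted and how promptly late events are found, in a trial that adds an anticoagulant to ASA. Section 7.6 sets no formal stopping rules and leaves that judgement to the DSMB. The scheduled DSMB meeting (section 9.5.1) may come once about 20 participants have completed 90 days, and the expedited reporting clocks in section 7.5.3 start on awareness. An event first heard of at month 6 could miss that DSMB report.

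**Working it through.** **1. Day of the last dose (sections 5.3.1, 5.3.2).**
- Clopidogrel and ASA: 1 + 89 = day 90.
- Rivaroxaban: 90 days from Day 1. With doses every 12 hours, a first dose 6 to 8 hours after the procedure, and procedure end times assumed between 06:00 and 16:00, 179 doses end on day 90 (just into day 91 for the latest start). A full 180 doses end on day 91.

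**2. The protocol's own 48-hour point.**
- Clopidogrel and ASA: 90 + 2 = day 92.
- Rivaroxaban: day 92 to 93.

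**3. Can the stated end day be reproduced?** For day 90 to be at least 48 hours after the last dose, that dose must fall no later than 90 − 2 = day 88. Full dosing does not meet this, so the section 7 end day is not reproduced.

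**4. What falls in the gap.** Under full dosing the tail is about days 91 to 92, or 2 of 92 days (2.2%). If the calendar clause governs, tail events are outside the AE period. If the 48-hour clause governs, they are inside it. In both cases they are outside the bleeding endpoints, which stop at day 90.

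**5. Closing visit.** Earliest date: 90 − 14 = day 76. Latest: day 90. Two readings follow.

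| | Dosing continues to day 90 after an early visit | Treatment stops at the early visit |
|---|---|---|
| Treatment days after a day-76 visit | 90 − 76 = 14; 14/90 = 15.6%; 14 × 2 = 28 rivaroxaban doses | None |
| 48-hour point | About day 92, 16 days after the visit | 76 + 2 = day 78 |
| Is day 90 at least 48 h after the last dose? | No | Yes |
| Agrees with 90 days of dosing? | Yes | No, 14 days short |
| Is the visit at or after the 48-hour point? | No | No |

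The last row is the same in both columns. An on-time visit on day 90 with a day-90 dose also precedes the 48-hour point.

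**6. Next scheduled review.** Taking 6 months as 182.6 days (assumed), the month 6 window of ±30 days is about day 153 to day 213. From day 90 to the earliest month 6 contact is 152.6 − 90 = about 63 days. From a day-76 visit to the latest is 212.6 − 76 = about 137 days. That contact may be by phone.

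**The case against.** A reader might infer that bleeds late in treatment go uncollected, or that participants have no AE contact after day 76. The documents do not support either.

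- Bleeding is reviewed at months 6 and 12 (sections 6.2.5, 6.2.6, Appendix 1). Section 6.1 collects all outcome data through 12 months, and section 9.5.4 has bleeding adjudicated.
- Section 7.5.1 and the Appendix 1 AE row support AE questioning at months 6 and 12. Section 7 also allows participant report and chart review, and section 6.2.1 teaches participants the signs of bleeding and gives them study contact numbers.
- The windows go by when the event happens, not when it is learned of. A day-80 bleed first reported at month 6 still belongs in the AE period and in the day 1 to 90 endpoint.
- The 14-of-90 figure needs both a visit at the edge of its window and dosing to day 90 afterwards. Section 6.2.4 can be read as stopping drug at the visit, and then no treatment days follow it.

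All of this stands. It reduces the day 77 to 90 problem to late ascertainment. It is also tempting to say that one missed bleed moves an arm of 20 by 5 percentage points. That is true of any missed event, so it is not an estimate of impact. No probability of a miss can be derived from the documents. The window is the same in both arms, so no direction of bias is shown.

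The objection does not remove the day-90 and 48-hour contradiction, the uncounted tail, or the conflict over AE review at months 6 and 12. The synopsis and sections 6.2.5 and 6.2.6 point one way on that, and section 7.5.1 and Appendix 1 the other.

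**Conclusion.** The concern holds as an internal contradiction with a limited consequence, and it should be corrected.

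- **Firm.** Under full dosing, day 90 cannot be at least 48 hours after the last dose. The 48-hour point is about day 92 (day 92 to 93 for rivaroxaban). Events on about days 91 to 92 lie outside the day-90 AE limit and the bleeding endpoints.
- **Firm.** Under either reading of section 6.2.4, the closing visit does not reach the 48-hour point, and the next scheduled contact is at month 6.
- **Conditional.** If the visit is on day 76 and dosing continues to day 90, up to 14 of 90 treatment days follow it. Bleeds on those days can still be captured and counted, but perhaps only by recall 63 days or more after day 90. Minor bleeding in section 8.1.2.2 depends on a measured hemoglobin fall or on details of care, which phone recall is likely to capture poorly. Non-bleeding AEs on those days rely on section 7.5.1 and the Appendix 1 row, against the synopsis and sections 6.2.5 and 6.2.6.

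The firm points rest on dosing as written in sections 5.3.1 and 5.3.2. The conditional one also assumes the extreme edge of the visit window.

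**What to change.** 1. Define one collection period for AEs and bleeding that runs to the protocol's own 48-hour point after each participant's actual last dose. Use it in the synopsis, section 7 and items 8 and 9 of section 8.1.2.
2. Schedule one AE and bleeding contact at or after that point. A phone call is enough.
3. Reconcile the visit window and the treatment-stop sentence in section 6.2.4 with the dosing length in sections 5.3.1 and 5.3.2 and the drug return in section 5.6. When dosing ends is for the sponsor to settle; the collection period then follows from it.
4. State whether AEs are asked about at months 6 and 12, and bring sections 6.2.5, 6.2.6 and 7.5.1, the synopsis and the Appendix 1 AE row into line.

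Cost: protocol wording and one short phone contact for each of the 40 participants.

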7.1 DEFINITIONS

7.1.1 Adverse Events

An Adverse Event (AE) is any untoward medical occurrence in a participant administered at least one dose of study medication; the event does not necessarily have a causal relationship with that treatment or usage. An adverse event can therefore be:

- any unfavorable and unintended sign, symptom or disease temporally associated with the use of a medicinal product, whether or not considered related to the medicinal product
- pre-existing symptoms or conditions which worsen during a study.

7.1.2 Post-procedure adverse events

Bruising and discomfort at the puncture site is expected in the first week after the PTA procedure and will not be collected as an adverse event.

7.1.3 Serious Adverse Events

Serious Adverse Event (SAE)

- An event that results in death
- An event that places the participant at immediate risk of death (a life-threatening event). This does not include an event that, had it occurred in a more severe form, might have caused death.
- Requires participant hospitalization or prolongation of existing hospitalization. For this study, the following exceptions apply to the index hospitalization:
 - The index hospitalization for PTA procedure will not be recorded as a serious adverse event
 - Prolonged hospitalization after the index hospitalization will not be recorded as a serious adverse event unless the prolongation is secondary to complications related to the study medication.
 - Hospitalizations for routine procedures and investigations are not considered a SAE in this protocol.
- Results in persistent or significant disability/incapacity. For this study, the following exception applies to this criterion:
 - Disability/incapacity secondary to tissue loss (amputation) is not considered a SAE for this protocol.
- Is a congenital anomaly/ birth defect

- Other medically important events that, in the opinion of the Site Investigator, may jeopardize the participant or may require intervention to prevent one of the other outcomes listed in the definition above.

Some conditions may not be immediately life threatening or require hospitalization. Should the investigator feel that the event may jeopardize the participant or may require intervention to prevent more serious outcomes, then it should be treated as serious.

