4 STUDY DESIGN

This is an open label single center randomized controlled pilot study.

4.1 INCLUSION CRITERIA:

1. Written informed consent and able to comply with protocol.
2. Infra-inguinal PAD presenting as CLI defined with Rutherford category of ≥ 1 .
3. More than 50% stenosis in the target infrainguinal vessel
4. Participant must be a good candidate for PTA using POBA (plain old balloon angioplasty) with or without stenting defined as TASC a, b, c and d lesions.

4.2 EXCLUSION CRITERIA:

1. Acute limb-threatening ischemia (e.g. embolic disease)
2. Hybrid procedures
3. Creatinine clearance <30 mL/min
4. Platelet count $<100 \times 10^9/L$; Hbg < 100 g/L.

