7.3 CAUSALITY

Relationship of all adverse events and serious adverse events to the study interventions (causality) should be assessed by the investigator as follows:

- **Unrelated:** There is not a reasonable possibility that the adverse event may have been caused by the study drug.

- **Possibly related:** The adverse event may have been caused by the study drug, however there is insufficient information to determine the likelihood of this possibility.
- **Related:** There is a reasonable possibility that the adverse event may have been caused by the study drug.

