9.4 DATA MANAGEMENT

Data will be recorded on a paper case report form (CRF) by the research personnel according to the protocol. CRFs will be verified for completeness and accuracy by a research team member not involved in the data collection. Any changes to the CRF will be tracked. Upon completion of data collection and verification of the CRF by the Investigator or designee, data will be entered in an data analysis software. Data will be cleaned and coded prior to analysis by a statistician. Missing data will be queried. Data still missing after queries will be coded appropriately by the statistician. Reports will be prepared prior to Data Safety Monitoring Board (DSMB) meetings including: enrollment per treatment arm, descriptive statistics for demographic data (and other relevant characteristic) to assess that randomization was effective, and a tabulated summary of AEs and SAEs per treatment arm.

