9.5.4 Adjudication of outcomes

The primary outcome, bleeding events and major adverse cardiovascular events will be adjudicated by a blinded expert adjudication committee.

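### Under the prolongation criterion in 7.1.3, a longer index stay is an SAE only if the investigator, in an open-label trial, attributes it to study medication, so part of the DSMB's SAE table is filtered by causality

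*Combined protocol and SAP*

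**What the plan says.** Section 7.1.3 of the protocol lists admission, or prolongation of a stay, as one of its SAE criteria. Beneath that criterion it adds study-specific exceptions: "For this study, the following exceptions apply to the index hospitalization". One of them is that a prolonged stay is left out of the SAE record "unless the prolongation is secondary to complications related to the study medication".

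Other sections bear on this:

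- Section 7.1.1 defines an adverse event regardless of cause: "the event does not necessarily have a causal relationship with that treatment or usage".
- Section 7.3 makes causality a separate assessment, by the investigator, of events already recorded: "Relationship of all adverse events and serious adverse events to the study interventions (causality) should be assessed by the investigator as follows".
- Section 4 sets the blinding: "This is an open label single center randomized controlled pilot study".
- Section 7.5.3 says the DSMB will receive a table of every SAE before each scheduled meeting, irrespective of relatedness. Section 9.4 specifies the layout: "a tabulated summary of AEs and SAEs per treatment arm".
- Section 9.5.4 limits blinded review to named outcomes: "The primary outcome, bleeding events and major adverse cardiovascular events will be adjudicated by a blinded expert adjudication committee".

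**The concern.** Whether an event is serious is normally decided from what happened to the participant, and whether the drug caused it is decided afterwards. The exception reverses that order for one criterion. A longer index stay enters the SAE record by this route only once someone has decided that study medication was responsible, and in an open-label trial that person can be expected to know the arm.

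The exception applies just after arterial puncture, when study treatment begins: rivaroxaban 6 to 8 hours after the procedure, or a clopidogrel load on Day 1. One arm is labelled experimental and the other standard of care. Bias could run either way. Suspicion of the newer drug could raise its count, while a habit of blaming the procedure could lower it.

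What is at stake is the SAE table by arm. Section 7.6 sets no formal stopping rule and leaves the decision to the DSMB's discretion. Under 7.5.3 and 9.5.1, immediate notice to the DSMB covers only SAEs thought at least possibly related to study drug. The SAE table is therefore where the board would see serious events judged unrelated, and index-stay prolongations judged unrelated are missing from it unless they qualify some other way.

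**Working it through.** The plan states no rate of SAEs or prolonged stays, so there is no figure to reproduce. The check is mainly textual, followed by an illustration of size.

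**Order of the two judgements**

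1. 7.1.1: cause plays no part in whether something is an AE.
2. 7.3: causality is graded for all AEs and SAEs, so an SAE may be graded unrelated. Item 22 of the SAE form in Appendix 2 offers that grade.
3. 7.1.3, index-stay exception: a prolongation judged unrelated is never an SAE under this criterion, so it cannot reach the form by this route.
4. 7.5.3: the DSMB table is meant to include unrelated SAEs. Step 3 has already removed some of them, so the table is incomplete by construction.

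The threshold is also unclear. Section 7.3 has three grades (unrelated, possibly related, related), and the exception does not say on which side the middle grade falls.

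**Which events are exposed**

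- An event that prolongs the index stay is still an SAE if it is fatal, life-threatening, disabling (other than through tissue loss) or medically important. The last of these is itself investigator opinion.
- An untoward event behind an unrelated prolongation is still recorded as an AE under 7.1.1 and 7.5.1, and AEs are also tabulated by arm under 9.4.
- Bleeding that lengthens a stay is at least minor bleeding under 8.1.2.2 and is adjudicated blind, as are MACE and primary-outcome events (9.5.4).
- What remains is mainly non-bleeding, non-MACE, non-limb events (renal injury or infection, for example) that qualify as serious solely through a longer index stay.

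**Illustration of size**

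Expected recorded SAEs per arm = n × q × a, where n is participants per arm, q the true proportion with a prolonged index stay, and a the probability that a prolongation is attributed to study medication.

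Assumptions, none from the documents: n = 20 (section 8.2 gives a total of 40 and no allocation ratio is stated); q the same in both arms; a as shown, rivaroxaban v clopidogrel.

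| q | True prolongations per arm | a = 50% v 50% | a = 60% v 30% | a = 80% v 20% |
|---|---|---|---|---|
| 10% | 20 × 0.10 = 2 | 1.0 v 1.0 | 1.2 v 0.6 | 1.6 v 0.4 |
| 20% | 20 × 0.20 = 4 | 2.0 v 2.0 | 2.4 v 1.2 | 3.2 v 0.8 |
| 30% | 20 × 0.30 = 6 | 3.0 v 3.0 | 3.6 v 1.8 | 4.8 v 1.2 |

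For example, 20 × 0.30 × 0.60 = 3.6 and 20 × 0.30 × 0.30 = 1.8. With equal attribution the filter lowers both counts but creates no imbalance. With unequal attribution the recorded counts differ although the arms are identical.

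**The case against.** The strongest case against is that little is lost. The exception is deliberate and specific to this study, in patients whose procedure and disease often cause complications. It sits under one criterion. The events remain in the AE table that the DSMB also sees, so an event moves between two tables and does not disappear. The main safety and efficacy events for an antithrombotic after angioplasty are adjudicated blind. The SAE count is not among the primary or secondary outcomes in 8.1. Section 1.1 notes that angioplasty allows outpatient treatment, so prolonged index stays may be few. Even 3 recorded SAEs of 20 against 1 of 20 gives a two-sided Fisher p of about 0.6. Finally, study medication includes ASA in both arms and clopidogrel in one, so attribution need not favour either arm.

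Most of this stands as a limit on size. A reader might infer that SAE counts by arm as a whole rest on opinion, that events are concealed from the DSMB, or that the bleeding results are compromised. The documents support none of these: the other seriousness criteria, AE recording and blinded adjudication all still operate. Nor do they show that attribution would differ by arm; they show only that nothing in the SAE process guards against it.

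The objection does not remove the internal conflict. The plan describes the DSMB table as covering all SAEs irrespective of relatedness, and the definition prevents that. A board without a formal rule reads small counts directly, so a non-significant p-value does not make the filter harmless.

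**Conclusion.** The point holds within a narrow scope. For the prolongation criterion at the index stay, 7.1.3 puts causality ahead of seriousness, contrary to 7.1.1 and 7.3. The SAE table promised to the DSMB in 7.5.3 is incomplete as a result, and open to differential attribution by arm. The affected events are those that meet no other seriousness criterion, mainly those that are not bleeding, MACE or limb events. No listed outcome is affected.

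The size cannot be estimated from the documents. Under the assumed 20 per arm and 10% to 30% true prolongation, attribution of 60% v 30% would produce a spurious gap of about 0.6 to 1.8 recorded SAEs (1.2 − 0.6 and 3.6 − 1.8). These figures show the mechanism and are not a forecast. That the judging investigator knows the allocation is inferred from the open-label design.

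**What to change.** Replace the prolongation exception in 7.1.3 with one sentence that does three things:

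- records as an SAE every prolongation of the index stay that results from an untoward medical event;
- leaves causality to be graded separately under 7.3;
- exempts only prolongations with no untoward event, such as planned or logistic delays.

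This makes the table in 7.5.3 match its description, and the position of the middle causality grade no longer affects whether a prolongation is recorded.

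The cost is a few more SAE forms and slightly more reports to the ethics board and the drug supplier. Health Canada expedited reporting is unchanged, because 7.5.3 already restricts it to unexpected SAEs that are at least possibly related. This assumes that the present exception is read as including possibly related events.

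The change reduces investigator judgement without removing it: someone who knows the arm still decides whether a stay was prolonged by an untoward event or by logistics. That is a narrower and more checkable question than whether the drug caused it.
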